## **Consent**

Informed consent will be conducted within the MyDataHelps app via an eConsent. A waiver of documentation of consent is requested to obtain electronic consent for this study.

If a patient is interested in participating, a study team member will invite them to the study using the RKStudio study portal email system. Participants will be directed to download the MyDataHelps app on their smartphone through the Apple or Google Play Store (dependent on smartphone), which will include an IRB-approved study consent module. When a participant opens MyDataHelps, they are first required to register an account using their email, and are subsequently presented with the eConsent form that lays out the process of participation. The patient is asked their name and for a finger-drawn signature. Study personnel will be available by phone or email to answer any questions participants may have about the consent and study. If participants do not complete the informed consent process via the study app and have not indicated that they do not wish to participate in the study, study staff will follow up by phone or email to answer questions or provide assistance.

Participants will have the option to download a copy of the consent document or have a copy emailed or mailed to them.

### **Enrollment**

Participants will complete several steps prior to enrollment being considered as “completed.”

Participants must complete the following steps to be enrolled in the study:

1. MyDataHelps study app download, installation, and account creation
2. Completion of informed consent
3. Completion of baseline survey via the MyDataHelps study app
4. Download and installation of assigned app-based intervention (Headspace or SilverCloud), if applicable
5. Receipt of device (Apple Watch or Fitbit) and agreement to wear the device regularly. Participants’ devices will be mailed, unless they indicated that they would like to meet with study staff to receive their device in person.
6. Pairing and setup of smartphone, device (Apple Watch or Fitbit), and MyDataHelps study app

Study staff are available by phone or email as necessary to provide technical support to aid participants in downloading apps, completing informed consent, or setting up their devices. Participants may also opt to meet with study staff in person, as described above.

Participants will be offered to complete consenting and enrollment steps remotely (via telephone with a study team member and on their own following their download of the MyDataHelps study app). If further assistance is needed, participants may opt to meet recruitment staff in person for support with downloading app(s), completing the informed consent process, completing the baseline survey, or picking up and configuring their Apple Watch or Fitbit. Patients who begin the recruitment process online may also opt to meet recruitment staff in person to complete the remainder of the process (e.g., informed consent, enrollment, downloading apps). In-person meetings may take place in a designated study space at Michigan Medicine or UHS or at an agreed-upon location in the community (e.g., coffee shop, campus library).

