### **Phase 1**

Patients with scheduled intake mental health appointments, pre-screening mental health appointments, on the waitlist/referral list, or identified as a potential patient seeking mental health care at Michigan Medicine or University Health Services will be recruited to participate in the study. Patients can be recruited at any time between the appointment being scheduled to up to one month following their intake appointment.

Participants that are enrolled with sufficient time before their scheduled appointment ( $\geq 2$  weeks) will be randomized to one of **three groups**:

- 1) Enhanced Feedback + Standard Feedback (**EF+SF**): Participants will receive enhanced feedback from the MyDataHelps study app in addition to standard feedback from the Apple Watch health app or Fitbit activity tracker
- 2) App-Based Intervention + Standard Feedback (**App+SF**): Participants will receive an app-based intervention in addition to standard feedback from the Apple Watch health app or Fitbit activity tracker
- 3) App-Based Intervention + Enhanced Feedback + Standard Feedback (**App+EF+SF**): Participants will receive an app-based intervention, enhanced feedback from the MyDataHelps study app, and standard feedback from the Apple Watch health app or Fitbit activity tracker

Some patients may have a shorter waiting period (<2 weeks) prior to their intake appointment (e.g., due to acute mental health symptoms). These patients will also be contacted for recruitment to provide opportunity for benefit from the research and from access to the mHealth interventions and will still be randomized to one of the above-listed groups.

As part of the enrollment process, participants will be guided by a study team member through **three processes**:

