1. **Download Study App:** Participants will download the study app, MyDataHelps, on their smartphone. MyDataHelps is a commercially available application developed by CareEvolution. This app serves as a vehicle for consent, data collection, delivery of all study questionnaires, automated notifications, and reminders. The app will also receive data from the Health app and study devices. Participants will be asked to complete daily mental health symptom assessments via the app throughout the duration of their enrollment in the study. The app will also present enhanced feedback on participant progress via a personalized “dashboard.” If participants are utilizing an Apple Watch with their existing iPhone, they must enable MyDataHelps to read out the data fields in the Health app. This will be made clear to

participants during the consent process, so a participant can decide if they are still interested in participating.

2. **Receive Device:** Participants will be provided with an Apple Watch or Fitbit to sync with their smartphone. Participants with iPhones will be provided with Apple Watches or Fitbits and participants with Androids will be provided with Fitbits, or similar smart watches and activity trackers for both types of phones. This device will be worn throughout their entire involvement in the study. This will allow for collection of objective data on daily activity, such as steps/physical activity, sleep, and heart rate.
3. **Download App-Based Intervention:** Participants randomized to the groups receiving app-based interventions will download additional apps to their smartphones that are designed to address mental health symptoms. Participants will be computer-assigned to one of the two app-based interventions (mindfulness via the Headspace app or cognitive behavioral therapy via the SilverCloud app). A study team member will guide them through the process of downloading the app to their phone at that time.

Participants will also be asked for permission for the study team to collect active (e.g., symptom self-reports) and passive (e.g., screen time) data through their smartphone through the duration of the study.

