### Surveys

Participants will be asked to complete four surveys, including a baseline survey at the time of enrollment and three follow-up surveys, which will be designed to complement in-clinic assessments completed as a part of standard outpatient mental health care. To the extent possible, redundancy with in-clinic assessments (i.e., due to the Measurement-Based Care program) will be avoided. The first follow-up survey will occur at the end of 6 weeks post-enrollment, the second at the end of 18 weeks post-enrollment and the third at the end of 12 months post-enrollment.

Depending on waitlist length for outpatient mental health services, there may be variation in whether participants have engaged with clinical care by the time they complete their follow-up survey(s). Surveys will be administered by the predetermined schedule regardless of whether participants have engaged with care. The rationale for this decision, rather than scheduling follow-up surveys to coincide with the initiation of outpatient care:

1. There is a possibility that participants may never engage with outpatient care, and these non-engagers would never receive follow-up surveys
2. Waitlist time often varies between recruitment sites (i.e., UHS tends to have a shorter waitlist for care), which would create measurement biases (e.g., UHS patients may consistently engage in care with less time to engage with the app-based intervention)
3. Participants may be receiving other mental health care (e.g., via primary care), making it less important to time follow-up surveys with the initiation of outpatient mental health services
4. The existing timeline ensures all participants randomized to the groups receiving app-based interventions have received a reasonable 'dose' of the intervention prior to assessment
5. The existing timeline ensures that measurement will take place at generally the same time frame for all participants

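### Installing the assigned app is a condition of enrolment that only the app arms face after assignment, and survey dates run from enrolment, so app versus EF+SF comparisons risk selection bias of unknown size and direction

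*Combined protocol and SAP*

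**What the plan says.** The Enrollment section introduces six steps with "Participants must complete the following steps to be enrolled in the study". They are the study app, consent, the baseline survey, the assigned intervention app, device receipt, and pairing. Step 4 reads "Download and installation of assigned app-based intervention (Headspace or SilverCloud), if applicable".

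Phase 1 describes this download as part of the enrolment process and as something done by people already allocated: "Participants randomized to the groups receiving app-based interventions will download additional apps to their smartphones". Enhanced feedback is delivered through MyDataHelps, which every arm installs at step 1, so EF+SF has no matching step.

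Follow-up is timed from enrolment. The Surveys section says "The first follow-up survey will occur at the end of 6 weeks post-enrollment", with the later surveys at 18 weeks and 12 months on the same clock. The Self-Report Surveys section repeats this.

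Two phrases point to another order. Phase 1 says that "Participants that are enrolled with sufficient time before their scheduled appointment" will be randomised, which puts enrolment before allocation. The Surveys section describes four surveys, "including a baseline survey at the time of enrollment and three follow-up surveys", which ties enrolment to step 3, before any app is installed.

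The Analysis Plan names t-tests and chi-square tests and calls feasibility and acceptability a primary goal. It defines no analysis population. No section states the moment of randomisation or a rule for people who are randomised but do not finish set-up.

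**The concern.** Aim 1 is about the effectiveness of the apps and of enhanced feedback, separately and combined. EF+SF is the only arm without an app, so every app versus no-app comparison runs through it. If being followed up depends on completing a step that follows allocation and exists only in the app arms, those arms are filtered on willingness or ability to install and EF+SF is not. Randomisation no longer protects that comparison, and a larger sample does not help.

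The second stake is feasibility. If enrolment requires installation, everyone enrolled in an app arm has installed the app by definition. People who declined or could not install it would then drop out of any app-use rate calculated among the enrolled. This needs no outcome difference between installers and non-installers.

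**Working it through.** The plan gives no figure to reproduce: the target of 4,500 has no stated alpha, power, effect size, SD or dropout. The check is therefore a comparison of the wording, followed by an illustration.

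**Order of events**

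- Enrollment, step 4: the app is already assigned, so allocation comes before enrolment is complete.
- Phase 1, download step: performed by people already randomised, so it agrees with step 4.
- Phase 1, randomisation sentence: enrolled people are then randomised, so enrolment comes before allocation. This cannot be squared with step 4.
- Surveys: baseline survey at enrolment. If the clock starts there, it starts at a step common to all arms.

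Two readings remain.

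- Reading A: enrolment means all six steps are complete. A randomised non-installer in an app arm then has no enrolment date and no survey due date.
- Reading B: enrolment is dated at the baseline survey. The clock then does not depend on the app, and the problem is much smaller.

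**Illustration under reading A**

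Assumptions, none from the documents except the 4,500 and the three arms: equal allocation; no true effect; two-sided 5% test; excess app-arm loss *p*; gap *d* (in SD) between the people lost and the people retained. I use n = 4,500 / 3 = 1,500 per arm, and also n = 750. The lower figure allows for unknown survey non-response, and for Phase 1 and App-Based Interventions disagreeing on whether people waiting under 2 weeks are in the randomisation.

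- Bias = p × d, at any sample size.
- SE = √(1/n + 1/(n(1 − p))).
- Type I error = Φ(−1.96 + bias/SE) + Φ(−1.96 − bias/SE).

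Worked case, p = 0.10, d = 0.3, n = 1,500: bias = 0.030; SE = √(1/1,500 + 1/1,350) = 0.0375; bias/SE = 0.80; type I error = 12.6%.

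| p | d | Bias (SD) | Type I error, n = 1,500 | Type I error, n = 750 |
|---|---|---|---|---|
| 2% | 0.1 | 0.002 | 5.0% | 5.0% |
| 2% | 0.3 | 0.006 | 5.3% | 5.2% |
| 5% | 0.3 | 0.015 | 6.9% | 5.9% |
| 10% | 0.1 | 0.010 | 5.8% | 5.4% |
| 10% | 0.3 | 0.030 | 12.6% | 8.7% |
| 20% | 0.3 | 0.060 | 34% | 19% |

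With d = 0.3, type I error reaches 10% at p of about 8% (n = 1,500) or 12% (n = 750). With d = 0.1 it takes 26% or 39%.

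**Limit of this model**

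It has one loss parameter, in the app arms. Device receipt and pairing (steps 5 and 6) apply to all arms, but they also follow allocation, and no blinding is described. Different kinds of people could leave each arm there, for instance EF+SF participants who learn that they get no app. Equal loss rates can still bias a comparison, so the net bias cannot be reduced to p × d.

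**Feasibility**

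If app-use rates are taken among installers and non-installers are non-users, the reported rate overstates the as-randomised rate by 1/(1 − p): 1.02, 1.05, 1.11 and 1.25 for p = 2, 5, 10 and 20%. At p = 10%, a reported 60% would be 0.60 × 0.90 = 54%. The plan defines no feasibility denominator, so this too is conditional.

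**The case against.** The strongest reply is that the Enrollment list is an onboarding checklist and not an analysis rule. Much of the protocol leans towards keeping people in. Survey reminders go to anyone who has not said they wish to stop, with no installation condition (Self-Report Surveys). Staff contact app-arm participants who are not using their app (App-Based Interventions). Deleting the study app is not withdrawal (Withdrawing). This stands as evidence of intent, but it does not settle the case of someone who never installs. The Withdrawing section also lets investigators remove people who no longer meet the inclusion criteria, one of which is willingness to keep the required configuration.

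A second reply is that the loss is probably small. Willingness to keep the set-up is screened, installation is guided, the apps are free, and the device (valued at about $120 to $250) is listed after the app step, which is a reason to finish it. This also stands. It makes the low rows of the table more plausible than the high ones, though the documents give no rate.

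A third reply is that the plan states no alpha and no primary hypothesis test, so type I error is a loose yardstick. That is fair, and the figures serve only to show scale.

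A reader might infer that the protocol drops non-installers, or that the app comparisons are already biased. The documents do not say so: they leave the order, the survey clock and the analysis set open.

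**Conclusion.** The point holds as a risk created by the plan's own definition. Read literally, the Enrollment section filters the app arms after allocation and leaves EF+SF without that filter, and the sections that point the other way do not resolve it. The comparisons exposed are App+SF and App+EF+SF against EF+SF. App+SF against App+EF+SF is largely unaffected, because both face the app step.

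Size and direction are unknown. Under the stated assumptions the effect on type I error is slight if nearly everyone installs or if non-installers resemble installers. It becomes material only when both loss and outcome gap are sizeable, roughly 10% and 0.3 SD at 1,500 per arm. The 34% figure should not be read as a prediction, since nothing in the documents supports 20% excess loss. Nor does it follow that only excess app-arm loss matters, because loss at the common device steps may differ in kind by arm.

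The feasibility consequence is more direct: under the literal definition, installation among the enrolled is 100% whatever people do. This should be fixed. Confidence is medium, because the harm depends on which reading the team follows.

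**What to change.** 1. Reconcile Phase 1, Surveys and Enrollment on one order: consent and baseline survey, then randomisation. Record app installation afterwards as an adherence and feasibility measure, not as a condition of enrolment.
2. Date the 6-week, 18-week and 12-month surveys in every arm from randomisation or from the baseline survey. This also serves the Surveys section's own fifth reason: "The existing timeline ensures that measurement will take place at generally the same time frame for all participants".
3. State in the Analysis Plan that everyone randomised is followed and analysed in the assigned group, whether or not the app was installed or the device set up.
4. Report completion of each set-up step by arm, with all randomised as the denominator.

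The cost is mainly wording, plus a new survey trigger date if the team now follows reading A. There are three downsides. Some payments and reminders will go to people without a working set-up. App effects will be slightly diluted, because non-installers stay in their arms. People slow to set up will have somewhat shorter app exposure before the 6-week survey. The last bears on the Surveys section's fourth reason, that "The existing timeline ensures all participants randomized to the groups receiving app-based interventions have received a reasonable" dose before assessment; recording the installation date would let the team report actual exposure at 6 weeks. If reading B is already the practice, little more than clarification is needed.

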### **Inclusion Criteria**

1. Must have a scheduled intake mental health appointment, pre-screening mental health appointment, on the waitlist/referral list, or identified as a potential patient seeking mental health care at Michigan Medicine or University Health Services
2. Age  $\geq$  18 years
3. Must have daily access to a smartphone to use for the study (iPhone 5s or later, depending on Apple Watch version available, or Android smartphone compatible with relevant Fitbit model and study app)
4. Understands English to enable consent and use of the MyDataHelps app and app-based interventions
5. Provide complete, updated contact information upon enrollment to the study
6. Agree to be contacted by study staff during the study
7. Willingness to keep study setup (devices, apps, settings) in required configuration for the duration of the study, and following instructions by study staff if required to update or re-achieve required configuration if required configuration has been lost (e.g., change of phone, app deletion)

### **Exclusion Criteria**

1. Deemed unable to provide informed consent (e.g., cognitive inability, guardianship)
2. Eating disorder, unless well controlled, as self-reported by the patient, verified by the research participant's mental health team, or review of medical chart by study team
3. Scheduled outpatient mental health appointment is a pediatric appointment (even if age 18+)
4. Wrist too large or too small to wear an Apple Watch or Fitbit comfortably (Note: bands that are shorter or longer than the standard will be made available to minimize this exclusion)

Those who have known allergies or previous reactions to fluorocarbon-based synthetic rubber, such as contact dermatitis with fluoroelastomer bands primarily used in wrist-worn fitness devices, will be offered an alternate Apple Watch or Fitbit band.

Participants may be excluded at the discretion of the Principal Investigators based on the determination that it is in the participant's or study staff's best interest (e.g., to fully ensure participant privacy in the case that a study staff member knows a patient or their family personally).

### **Participant Remuneration**

Participants will be remunerated \$20 for completing the baseline survey, \$20 for the first follow-up survey, \$40 for the second follow-up survey, and \$50 for the third follow-up survey. Participants could receive a total of \$130 for surveys via cash or gift card if they complete all study activities. Participants will be given an Apple Watch or Fitbit to use during their participation in the study and may keep these devices once they have completed the study. The Apple Watch Series 3 is valued at about \$250 and Fitbit Charge 3/Inspire HR valued at about \$120. Other versions of these devices or similar devices may be given to participants, based on availability. Between completion of surveys and receipt of Apple Watch, Fitbit, or similar devices, total participant remuneration will range from \$250 to \$380 via cash or gift cards and receipt of mobile health device, dependent on the mobile health devices available and received.

### **Required Device Configuration**

Participants will be guided through the study setup configuration requirements during the enrollment process. For the full study duration, participants will maintain the basic study configuration on their study devices (e.g., MyDataHelps, app-based intervention, Apple Watch or Fitbit synced with smartphone). Study staff will reach out to participants if non-compliance with study configuration is noted and will offer re-education or help to resolve technical problems. In interactions with participants, study staff will remind participants to ensure their devices are compliant with required device configuration. Notifications in MyDataHelps will support the participant in maintaining the required device configuration by sending update reminders.

A small minority of participants may experience study hardware or software problems. We may contact these participants to troubleshoot the problems via phone, letter, or email. An in-person meeting with study staff will be offered for further troubleshooting, if needed. If study tasks are completed successfully, these issues will have no effect on their compensation. However, if participants are unable to complete study tasks (e.g., follow-up surveys) due to these issues, their compensation may be impacted.

### **ASSESSMENT METHODS AND MEASURES**

This study will combine the following sources of information about participants:

- 1) Self-report surveys
- 2) Michigan Medicine and UHS electronic health records and other medical records data
- 3) Biological specimen

- 4) Passive and active data collected from participants' phones, linked sensors (Apple Watch or Fitbit), or use of app-based interventions (SilverCloud or Headspace)

### ***Self-Report Surveys***

Participants will complete four surveys, including a baseline survey and three follow-up surveys. All surveys will be self-administered via the MyDataHelps study app. In the case of technological difficulties, the study team does have paper copies of the baseline and follow-up surveys available, and the surveys may be administered in person or by phone. The baseline survey will take about 25 minutes. Survey questions include demographics, overall physical and mental health symptoms and diagnoses, substance use, environment, use of mobile technology and health apps, and social network and support. For each of the three follow-up assessments, participants will complete an approximate 20-minute survey with similar content as the baseline survey. If necessary, the survey can be administered by study staff via phone who will read survey questions to the participant and record their responses. When participants are due for their surveys, they will receive an email or app notification that their survey is available via the MyDataHelps app. If participants do not respond to the questionnaires, and have not indicated that they do not wish to participate in the study, a reminder will be sent by email, phone, mail, or text message.

The first follow-up survey will occur at the end of 6 weeks post-enrollment, the second at the end of 18 weeks post-enrollment, and the third at the end of 12 months post-enrollment. Each of these time-points may occur near the time of an in-person outpatient mental health clinic appointment, at which participants may be asked to answer some of the same questions that are contained in the study surveys. To reduce participant burden, study staff will monitor upcoming appointments and participants will receive a version of the survey without redundant items if they have an appointment within 1 week of their follow-up survey due date. They will still complete the remainder of the follow-up survey and be paid the same amount for their time. Additionally, participants who do not show for clinic appointments will still be able to complete the follow-up assessments via standard study procedure.

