## **Screening and Recruitment**

Participant screening and recruitment will be managed by study staff. All study team members are required to complete team/study training and all appropriate regulatory training and disclosures.

The study will recruit 4,500 participants via patients at Michigan Medicine and student patients at University Health Service (UHS). Potential study participants will include adult patients (age 18+) that are scheduled for an intake mental health appointment, pre-screening mental health appointment, on the waitlist/referral list, or identified as a potential patient seeking mental health at either Michigan Medicine or UHS. These appointments are generally scheduled with a 3-10 week waiting period. Patients will be invited to participate in the study as soon as possible after scheduling their appointment in order to best maximize participation during their full waiting period.

A waiver of HIPAA authorization is requested in order for study staff to:

- 1) Receive daily lists of patients for whom a mental health intake appointment has been scheduled at each recruitment site
- 2) Access the Michigan Medicine and UHS electronic health records to confirm eligibility of listed patients and obtain contact information

Study staff will employ the following **recruitment strategies** to contact, screen, and enroll potential participants:

1. At the time of scheduling their intake mental health appointment, patients may be informed by call center staff that they may be contacted about a new study.

2. Daily lists of newly scheduled appointments and individuals on the waitlist/referral list will be generated by the Michigan Medicine Department of Psychiatry call center, UHS scheduling, or from the Research Data Warehouse (RDW) and provided to study staff.
3. Using existing Research Data Warehouse information, a patient is prospectively identified as someone who meets the study criteria during the screening process. Potentially eligible patients may be contacted by email/text message/phone call to introduce the study, with an invitation to contact the study team by phone or email if interested in participating.
4. Prior to contacting patients by phone/text message/phone call, study staff will complete preliminary screenings via listed patients' electronic health records to determine whether basic, objective inclusion criteria are met (e.g., scheduled outpatient mental health appointment, age 18+).

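### Follow-up survey items are dropped because a clinic visit is near, not because a clinic score is on file, so the availability, setting and date of some scores depend on contact with care

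*Combined protocol and SAP*

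**What the plan says.** All references are to the combined protocol and SAP.

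- **Self-Report Surveys** sets the rule for the 6-week, 18-week and 12-month surveys: "participants will receive a version of the survey without redundant items if they have an appointment within 1 week" of the due date. The reason given is participant burden: a clinic visit may fall near the survey, "at which participants may be asked to answer some of the same questions that are contained in the study surveys". The default mode is stated as "All surveys will be self-administered via the MyDataHelps study app", with paper, in-person and telephone back-up.
- The same section adds that "participants who do not show for clinic appointments will still be able to complete the follow-up assessments via standard study procedure".
- **Surveys** states the general policy that, as far as possible, "redundancy with in-clinic assessments (i.e., due to the Measurement-Based Care program) will be avoided". It also explains why surveys run on a fixed calendar whether or not care has started. Among the reasons are waitlists that differ by site and the aim that "measurement will take place at generally the same time frame for all participants".
- **Table 1** schedules the PHQ-9, GAD-7, PCL-5 and other scales at all three follow-up times and mentions no exception.
- **Assessment Methods and Measures** and **Electronic Health Record Data** list health record data as a study source.
- **Analysis Plan** proposes t-tests and chi-square tests. It has no rule for missing scores or for scores from two sources.

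**The concern.** The study gives up its own measurement in exchange for one it does not control. The short survey is issued because a visit is booked. Nothing requires that a clinic score exists, and the wording on what the clinic asks is conditional.

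The plan does not name the overlapping items, say that a clinic score replaces the survey score, set a date window for it, or tell the analyst how to combine sources. If symptom scales are among the items, then whether a participant has a score, where it was taken and on which day all depend on contact with care. The fixed calendar was chosen to remove that dependence.

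The effect is most direct in Phase 2, where care is the exposure under study, and in comparisons between sites, whose waits differ. At 18 weeks and 12 months, having a visit nearby is a post-randomisation event that may reflect symptoms and engagement.

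**Working it through.** The documents give no figure for the share affected, and no alpha, power, effect size or dropout rate, so there is no stated figure to reproduce. The check has two parts: what the rule leaves open, and an illustration of size.

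**1. Cases under the rule**

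| Situation at the due date | Items in study survey | What the plan provides |
|---|---|---|
| No appointment within 1 week | Yes | Nothing further needed |
| Appointment attended, form completed | No | Score may be in the health record; no substitution rule or date window |
| Appointment attended, form not completed | No | Nothing |
| Appointment missed | No, if the short version was issued | Standard procedure stays open; no step described for re-sending the omitted items |

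**2. Share with intake in the 6-week window**

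Input from Screening and Recruitment: "These appointments are generally scheduled with a 3-10 week waiting period". Assumptions: waits uniform over that range, enrolment 0 to 3 weeks after scheduling (lag L), intake visits only.

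Time from enrolment to intake is then uniform on (3 - L, 10 - L), an interval 7 weeks long. For every L from 0 to 3 it contains weeks 5 to 7.

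- Visits either side of the due date (weeks 5 to 7): 2/7 = 28.6%.
- Visits in the week after only (weeks 6 to 7): 1/7 = 14.3%. The text supports this reading too, since staff are said to monitor upcoming appointments.

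These shares apply to participants who have such a wait ahead of them. The Phase 1 section also admits people with waits under 2 weeks, people up to one month after intake, and people only on a waitlist or referral list. For those past intake the intake share is lower; later clinic visits would add to the share.

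**3. Scores lost**

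Assume the clinic form is not completed at 10% to 40% of these visits (no source in the documents).

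- Narrow window: 0.143 x 0.10 = 1.4%, to 0.143 x 0.40 = 5.7%.
- Wide window: 0.286 x 0.10 = 2.9%, to 0.286 x 0.40 = 11.4%.

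**4. Effect on precision**

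Assume equal arms of 4,500/3 = 1,500, two-sided alpha 0.05, 80% power, and the shares above applied to everyone. The detectable standardised difference is (1.960 + 0.842) x sqrt(2/n).

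- No loss, n = 1,500: 0.102.
- Loss of 11.4%, n = 1,500 x 0.886 = 1,329: 0.109.
- Every item in the window lost: n = 1,286 (14.3%) gives 0.110; n = 1,071 (28.6%) gives 0.121.

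**5. Effect on an arm comparison if all scores are recovered**

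Bias = (clinic minus app shift in score) x (difference between arms in the share of clinic-sourced scores). With an assumed shift of 0.5 to 2 points and a difference of 0 to 10 percentage points, the bias runs from 0 to 2 x 0.10 = 0.2 points. It is zero if the shares are equal.

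The documents give no visit frequency after intake, so no share is offered for 18 weeks or 12 months.

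**The case against.** The rule is deliberate and has a stated purpose. The surveys are meant to complement clinic assessment, health record data are a listed source, and no-shows keep access to the assessments. The calendar promise is only of generally the same time frame, and a shift of up to a week fits it. Mode already varies for other reasons (paper, telephone, Qualtrics). The rule is the same in all arms. The size rests on assumed inputs, and even the upper end of the assumed loss moves the detectable difference only from 0.102 to 0.109.

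Much of this stands, and it rules out several stronger readings that a reader might infer:

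- *That the PHQ-9 and GAD-7 are certainly dropped.* The documents say only that redundant items are removed and never list the clinic forms.
- *That every missed visit means a missing outcome.* The no-show provision addresses this, although it describes no step for re-sending items.
- *That the Analysis Plan makes the PHQ an arm-comparison outcome.* It names the PHQ only in the genotype analyses; its t-test and change-score sentences name no scale.
- *That the randomised comparison is biased.* That would need contact with care, or clinic form completion, to differ by arm or relate to outcome. Nothing in the documents shows it.

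The objection does not answer the attended visit where no form was completed. Permission to use health records is also not a rule for substituting one score for another.

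**Conclusion.** The concern holds as a flaw in a stated rule. Followed as written, the rule removes scheduled items without a clinic score in hand, and it ties the availability, setting and date of the affected scores to contact with care. That works against the plan's own reason for a fixed schedule.

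The likely size at 6 weeks is modest: about 1-11% of scores lost among participants with a 3-10 week wait ahead. This rests on uniform waits, intake visits only, and an assumed 10-40% of clinic forms not completed. The loss of precision is small. The larger problem is that the loss and the change of source fall on people who are in contact with care, which matters most for Phase 2 and for site comparisons. For the randomised arms, bias at 18 weeks and 12 months is a possibility and no more. That symptom scales are affected is a reasonable inference, not a documented fact. The daily mood item is untouched.

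**What to change.** Amend the Self-Report Surveys section so that the PHQ-9 and GAD-7 stay in every 6-week, 18-week and 12-month survey regardless of appointments. Trim only other overlapping items. State that the study-survey score is the outcome and that clinic scores serve only as auxiliary data, for example to inform the handling of missing survey scores.

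The cost is a change to the survey logic and, by estimate, a few extra minutes for participants with a nearby appointment, within a survey of about 20 minutes. Payment is already the same for the short and full versions. Staff would have less switching of versions to manage. If these two scales turn out to be the only overlap, the change in effect withdraws the short version.

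If the sponsor prefers to keep the rule, the minimum is to name the redundant items, state the substitution rule and date window, and say what happens after an attended visit without a completed form. The source, mode and date of each score should also be recorded, with a pre-specified sensitivity analysis by source.
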